6.2.2. Physical activity metrics

- ✓ The same analysis for other physical activity metrics (steps, MVPA time) is performed as for Sedentary time.
- ✓ The similar analyses of each physical activity metrics, as same as that for EORTC-QLQ-C30, are performed to assess the associations.

6.2.3. Association between EORTC-QLQ-C30 and Physical activity

- ✓ The Pearson's correlations between change in PRO and physical activity metrics will be calculated at each measurement time point.

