4. AMENDMENTS AND UPDATES

Document History

Document	Version Date	Rationale
Original protocol	1 June 2020	Not applicable (N/A)
Amendment 1	1 September 2020	
To clarify the role and responsibility for each organization in this study, descriptions in Section 2 and related sections were modified.
 
As PRO data collection for "palbociclib use" was removed, descriptions in Section 6 and related sections were modified.
 
Other minor edits were made.

Amendment 2	01 October 2021	
To update and change the research organization and responsible parties, description in Section 2 was revised.
 
To clarify that the target population in this study is a patient who initiates first or second line endocrine-based treatment, descriptions in Section 8.1, Figure 1 and 9.1.1 were revised.
 
Following the revised Japanese Breast Cancer Society Clinical Practice Guideline, the number of patients who initiate endocrine monotherapy in the first or second-line setting has decreased thus it has become difficult to accumulate patients in Group 2, and the number of patients in Section 9.1 has been revised accordingly.
 
Based on the comments from Independent Ethics Committee, descriptions were added in Section 15.1 and Section 19.1.

Amendment 3	20 December 2021	To update the planned dates of milestone based on actual enrollment speed, description in Section 5 and Section 9.1 were revised.

PFIZER CONFIDENTIAL

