6. SCHEDULE OF ACTIVITIES

Refer to STUDY PROCEDURES and ASSESSMENTS sections of the protocol for detailed information on each procedure and assessment required for compliance with the protocol.

Procedure / Assessment	Screening	Baseline	Observation period (6 cycles; 24 weeks) ^j		End of Study ^c
			Weekly ^a	Cycle-base ^b	
Time Window			+ 3 days ^d	+ 7 days ^d	
Informed consent	X				
CRF data					
Patient baseline characteristics; Demography, Height, Weight, Medical history, Prior treatment and surgery history, Primary diagnosis, Site of metastatic and disease, Menopausal status, Treatment being initiated, Line of therapy		X			
ECOG performance status ^k		X	↔X↔		X
Adverse event monitoring (eg, type, grade) ^e			↔X↔		
Treatment (eg, type, duration) ^f			↔X↔		
Palbociclib dosing modification ^g			↔X↔		
Concomitant Medication (Surgery, Radiotherapy)			↔X↔		
Disease progression (if applicable)			↔X↔		
Initial treatment discontinuation (if applicable)			↔X↔		
Study withdrawal (if applicable)			↔X↔		
Study completion					X
PRO data via smartphone-based application					
Patient baseline characteristics; Education, Employment		X ⁱ			
EORTC-QLQ-C30		X ⁱ		X	
PRO-CTCAE ^h		X ⁱ	X		
Overall satisfaction with treatment				X	

PFIZER CONFIDENTIAL

Procedure / Assessment	Screening	Baseline	Observation period (6 cycles; 24 weeks) ^j		End of Study ^c
			Weekly ^a	Cycle-base ^b	
Time Window			+ 3 days ^d	+ 7 days ^d	
Physical activity data via wearable device					
Physical activity		X	↔X↔		

- a. Weekly assessment of PRO-CTCAE will be conducted based on Cycle 1 Day 1 regardless of cycle delay.
- b. Cycle-based assessment of EORTC-QLQ-C30 and Treatment satisfaction will be conducted on Day 15 of each cycle.
- c. End of study is defined as end of 6 cycles of initiated treatment. If patients discontinue the initiated treatment before completion of 6 cycles (eg, due to disease progression) and switch to another treatment, end of study will be end of 24 weeks after initiation of initial treatment. In this case, to assess association between change in QOL and physical activity versus disease progression, data collection [including PROs (EORTC-QLQ-C30 and PRO-CTCAE) and physical activity evaluation, EDC data entry] will continue to the end of the study (ie, 24 weeks after the start of the study) even if the treatment is switched to another treatment.

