9. RESEARCH METHODS

9.1. Study design

The study is a prospective, multicenter, observational study to evaluate PRO and physical activity using smartphone-based application and wearable device in Japanese patients with HR+/HER2- ABC.

Patients will be enrolled into either palbociclib plus endocrine therapy group (Group 1) or endocrine monotherapy group (Group 2) based on the discretion of the treating physician under routine clinical practice. Total target number of patients is approximately one-hundred in this study (assuming about 20 to 80 patients in each group). The number of enrolled patients will be monitored, and the enrollment will be completed when 100 patients have been enrolled. Of note, the patient who is informed about this study for participation at the time when the number of enrolled patients reaches 100 is allowed to enroll. Enrolled patients will download a smartphone-based application for electronic PRO (ePRO), be provided access to and trained on the use of the application to complete baseline, weekly, and cycle-based assessments for 6 cycles (24 weeks). In addition, enrolled patients will be provided with wearable device and requested to wear the device at all-times, except of while bathing and sleeping, for 6 cycles (24 weeks).

[figure not shown]
In this study, one cycle is defined as follows;

- In Group 1 (palbociclib plus endocrine therapy), palbociclib is administered for 3 consecutive weeks followed by 1 week off treatment to comprise one cycle of 4 weeks. If palbociclib is temporarily interrupted (eg, due to adverse event) and the start of the next cycle is delayed, the duration of one cycle may exceed 4 weeks, then, the observation period may exceed 24 weeks.
- In Group 2 (endocrine monotherapy), one cycle is defined as 4 weeks.

Participation in this study is not intended to change the routine treatment that patients receive as determined by their prescribing clinicians; all treatment decisions and type and timing of disease monitoring are at the discretion of the treating physician. No additional visits to the clinic will be required for the purposes of the study.

Figure 1 summarizes the overall study design.

Figure 1. Study Design

It is anticipated that all data collection for this study will occur over a 24-month period (from the first patient's first visit to the last patient's end of study assessment),

Planned patient enrollment duration: 18 months

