2.1. Study Objectives, Endpoints, and Estimands

Primary objective

Assess change in (1) PRO as measured by EORTC-QLQ-C30 collected via smartphone-based application and (2) physical activity as measured by wearable device in Japanese patients with HR+/HER2- advanced breast cancer receiving below treatment as first or second line setting:

1. *Palbociclib plus endocrine therapy (Group 1) or*
2. *Endocrine monotherapy (Group 2)*

NOTE: The study is not intended to compare outcomes between the two groups as the primary objective.

Secondary objectives

The following research objectives will be addressed separately for both Group 1 and 2. When associations for group 1 and 2 are similar, the group 1 and 2 will be pooled.

- *Assess the association between change in EORTC-QLQ-C30 and physical activity versus investigator-reported adverse event (AE)*
- *Assess the association between change in EORTC-QLQ-C30 and physical activity versus patient-reported symptom as measured by PRO-CTCAE collected via smartphone-based application*
- *Assess the association between change in EORTC-QLQ-C30 versus change in physical activity*
- *Assess the association between change in EORTC-QLQ-C30 and physical activity versus disease progression*
- *Assess the feasibility of collecting physical activity data with the wearable device in Japanese patients with advanced breast cancer*
- *Assess patient's treatment satisfaction (collected as a single item via smartphone-based application)*
- *Evaluate concordance and discordance between investigator-assessed AE versus PRO-CTCAE*
- *Characterize patients with HR+/HER2- ABC initiating each group treatment (eg, baseline patient demographics and clinical characteristics)*

The following research objectives will be addressed Group I only.

- *Describe dosing patterns (eg, dose reduction, dose interruptions, cycle delay)*

CCI

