2.2. Study Design

The study is a prospective, multicenter, observational study to evaluate PRO (Health related QOL) and physical activity using smartphone-based application and wearable device in Japanese patients with HR+/HER2- ABC.

Patients will be enrolled into either palbociclib plus endocrine therapy group (Group 1) or endocrine monotherapy group (Group 2) based on the discretion of the treating physician under routine clinical practice. Total target number of patients is approximately one-hundred in this study (About 50 patients in each group).

[figure not shown]
Enrolled patients will download a smartphone-based application for electronic PRO (ePRO), be provided access to and trained on the use of the application to complete baseline, daily, weekly, and cycle-based assessments for 6 cycles (24 weeks). In addition, enrolled patients will be provided with wearable device and requested to wear the device at all-times, except of while bathing and sleeping, for 6 cycles (24 weeks).

In this study, one cycle is defined as follows;

- In Group 1 (palbociclib plus endocrine therapy), palbociclib is administered for 3 consecutive weeks followed by 1 week off treatment to comprise one cycle of 4 weeks. If palbociclib is temporarily interrupted (eg, due to adverse event) and the start of the next cycle is delayed, the duration of one cycle may exceed 4 weeks, then, the observation period may exceed 24 weeks.
- In Group 2 (endocrine monotherapy), one cycle is defined as 4 weeks.

Participation in this study is not intended to change the routine treatment that patients receive as determined by their prescribing clinicians; all treatment decisions and type and timing of disease monitoring are at the discretion of the treating physician. No additional visits to the clinic will be required for the purposes of the study.

Figure 1. Study Design

It is anticipated that all data collection for this study will occur over a 18-month period (from the first patient's first visit to the last patient's end of study assessment),

Planned patient enrollment duration: 12 months

Planned data collection for an individual patient: 6 cycles (24 weeks*)

*In Group 1, if palbociclib is temporarily interrupted (eg, due to adverse event) and the start of the next cycle is delayed, the duration of one cycle may exceed 4 weeks, then, the observation period may exceed 24 weeks.

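### The quality-of-life versus activity objective rests on a separate correlation at each time point: repeated pairs are not combined, the activity week is undefined, and a small group gets imprecise estimates

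*SAP*

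**What the plan says.** SAP 2.1 lists this secondary objective: "Assess the association between change in EORTC-QLQ-C30 versus change in physical activity". Its introductory lines state that "The following research objectives will be addressed separately for both Group 1 and 2" and add that "When associations for group 1 and 2 are similar, the group 1 and 2 will be pooled".

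The visible analysis is one sentence. SAP 6.2.3 plans Pearson "correlations between change in PRO and physical activity metrics will be calculated at each measurement time point", and Protocol 12.5.2 has the same wording. Neither place mentions a confidence interval, a summary across cycles, or a model.

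The two measures follow different calendars. Footnote b of Protocol section 6 reads: "Cycle-based assessment of EORTC-QLQ-C30 and Treatment satisfaction will be conducted on Day 15 of each cycle". Footnote d keeps that form open for up to 7 days. There are six cycles. Activity is averaged by week (SAP 6.1.2.1), and SAP 3.1 requires at least 5 days with 10 or more hours of wear for a week to count.

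On group size, Protocol 9.1 has "assuming about 20 to 80 patients in each group", while SAP 2.2 still has "About 50 patients in each group". The entry for Amendment 2 in Protocol section 4 explains that "it has become difficult to accumulate patients in Group 2".

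**The concern.** The study collects QLQ-C30 every cycle and activity continuously, and SAP 6.1 already fits repeated-measures models to both primary endpoints. The objective that links the two measures is where the repeated pairs would be most informative, yet they are not brought together there.

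Each planned correlation uses one pair per patient and compares patients with one another at one cycle. None of them asks whether a patient's quality of life is lower in the cycles in which her own activity is lower. The correlations are not independent of each other either: the same patients contribute to all six, and all six changes are measured from the same baseline value.

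The rule also cannot be programmed as written. A once-per-cycle questionnaire and a weekly average have no common time point until the SAP names one. Day 15 opens the third week of a cycle and the form may be completed up to 7 days later, so Days 8 to 14 and Days 15 to 21 are both plausible, as is a mean over the cycle.

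At stake is a grid of noisy, overlapping correlations with no summary. A reader could take chance variation between cycles for a time course, or take a wide null result in a small group for absence of association.

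**Working it through.** The plan states no power, precision or expected correlation for this objective, so there is no figure of its own to reproduce.

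**Inputs.** Group sizes are 20 and 80 (Protocol 9.1), 50 (SAP 2.2) and 100 if pooled (Protocol 12.1). There are k = 6 post-baseline questionnaires. Assumptions: an observed r of 0.3 for illustration, and two-sided 95% intervals as used for the primary endpoint means. That Group 2 is near 20 is also an assumption; it rests on the accrual note in Protocol section 4.

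**One time point.** The Fisher interval is tanh(atanh(r) ± 1.96/√(n-3)), with atanh(0.3) = 0.310.

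| n | half-width on z scale | 95% CI for r = 0.3 | smallest \|r\| excluding zero |
|---|---|---|---|
| 20 | 1.96/√17 = 0.475 | -0.16 to 0.66 | 0.44 |
| 50 | 1.96/√47 = 0.286 | 0.02 to 0.53 | 0.28 |
| 80 | 1.96/√77 = 0.223 | 0.09 to 0.49 | 0.22 |
| 100 (pooled) | 1.96/√97 = 0.199 | 0.11 to 0.47 | 0.20 |

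**Within-patient estimate.** The repeated-measures correlation has df = n(k-1)-1 and a half-width of 1.96/√(df-1), assuming independent residuals and a common within-patient correlation.

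| n | pairs per patient | df | 95% CI for r = 0.3 |
|---|---|---|---|
| 20 | 6 | 99 | 0.11 to 0.47 |
| 20 | 4 | 59 | 0.05 to 0.51 |
| 50 | 6 | 249 | 0.18 to 0.41 |
| 80 | 6 | 399 | 0.21 to 0.39 |

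**Less favourable assumptions.** By simulation (true r of 0.3 both between and within patients, equal between- and within-patient variance), the standard deviation of the estimate, single time point against within-patient, is about:
- n=20, complete data: 0.21 against 0.09
- n=20, serial correlation 0.6 and 30% of cycles missing: 0.26 against 0.13
- n=50, complete data: 0.13 against 0.06
- n=80, complete data: 0.10 against 0.045

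The spread is roughly halved in each setting. Serial correlation and missing cycles reduce the gain but do not remove it.

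**Reading across cycles.** In the same simulation with complete data, the highest and lowest of the six per-cycle correlations differ on average by just under 0.5 at n=20 and just under 0.3 at n=50, although the true value is constant. With no association at all, at least one of six correlations at n=20 is nominally significant in 18% to 26% of simulated studies (intraclass correlation 0.8 down to 0.3).

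**Number of results.** Sedentary time, steps and MVPA × 6 cycles × 2 groups = 36 correlations for global health status alone. SAP 6.2.3 does not name the scales. The six scales used for the associations in SAP 6.2.1 would give 6 × 36 = 216, and all 15 scales 15 × 36 = 540, which is an upper bound.

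**Judging similarity for pooling.** With groups of 20 and 80, the standard error of the difference between two Fisher z values is √(1/17 + 1/77) = 0.268. Differences up to 1.96 × 0.268 = 0.525 are therefore compatible with equal correlations. If the larger group shows 0.3, anything from about -0.21 to 0.68 in the smaller group falls inside that band (tanh of 0.310 ± 0.525).

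**The case against.** **The study is descriptive.** Protocol 12.1 rules out hypothesis testing, SAP 5.1 gives description as the aim, and no test or interval is planned for these correlations. This stands: failing to separate 0.3 from zero misses no stated target. But a description is only as useful as its precision, and none is reported here.

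**The planned method matches the written objective.** Correlating the two changes from baseline at each cycle does estimate change against change. This stands too, so the added model should stay on the change-from-baseline scale. Subtracting a patient's baseline does not alter her deviations from her own mean, so this choice affects only the between-patient part.

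**The SAP allows pooling.** At n=100 one correlation of 0.3 already has an interval of 0.11 to 0.47. This would largely answer the precision point, but the SAP does not define similar, and two small sets of correlations cannot settle it. Pooling also leaves the within-patient question and the pairing week open.

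**The comparison favours the alternative.** The two estimates answer different questions and agree only if the between- and within-patient associations are equal. For an overall correlation mixing both, the gain at n=20 is smaller: the effective n is about 38 at an intraclass correlation of 0.7 and about 30 at 0.8.

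A reader might infer that the plan discards the repeated pairs, or that Group 2 could show no association at all. The documents support neither. Every pair enters one of the correlations; what is missing is their combination. At n=20 an observed |r| of about 0.44 or more excludes zero, and r = 0.5 has an interval of 0.07 to 0.77. Nor is 20 stated as the size of Group 2; it is the low end of a range.

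**Conclusion.** The point holds as a worthwhile, inexpensive improvement. In the visible text, the objective is assessed only by cross-sectional correlations that do not combine a patient's repeated pairs, and the activity week is undefined. The pairing gap stands at any group size.

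The precision problem is conditional. It applies to a group near 20 that is analysed without pooling, where each correlation cannot separate a weak or moderate association from none. At 50 or 80 an observed 0.3 already excludes zero, though a within-patient estimate would still be about twice as precise under the assumptions above. Those intervals are for correlations, and the model proposed below reports slopes, so they indicate the relative gain only.

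Parts of the SAP are blacked out (in 5.2 and after 6.1.2.2 and 6.2.6), and a further association analysis may sit there. The conclusion covers the visible text only.

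**What to change.** In SAP 6.2.3:

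1. Pair each cycle's QLQ-C30 with one SAP-defined weekly activity average, subject to the valid-wear rule in SAP 3.1. State whether it is the study week that contains completion of the questionnaire or the week immediately before it.
2. For each scale-metric pair, by group and also pooled if the SAP's pooling rule applies, add one repeated-measures model of change from baseline in QLQ-C30 on change from baseline in activity. Include a patient random intercept and cycle, and split activity change into the patient's mean and her deviation from it. Report both coefficients with 95% CIs as the summary estimate of association.
3. Keep the per-cycle Pearson correlations as description, each with a 95% CI.

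Naming the scales and metrics covered, and saying how similarity will be judged before pooling, would complete the section.

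The cost is SAP wording and modest programming, with no new data and no added burden on patients. The downside is that two coefficients must be explained in place of a simple correlation.

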6.2.4. Patient satisfaction

- ✓ Patient satisfaction will be summarized descriptively through tabular displays of frequency distributions of categorical variables, by measured points.

6.2.5. Adverse events and PRO-CTCAE

- ✓ Investigator-reported AE and patient-reported AE will be summarized.
- ✓ Association between investigator-reported AE and patient-reported AE will be assessed using contingency table and weighted Kappa coefficient.

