- d. Weekly-based assessments will remain open for up to 3 days (72 hours) and cycle-based assessments will remain open for up to 7 days (168 hours).
- e. Safety reporting will follow applicable regulations and is detailed in Section 16.
- f. Type and duration of treatment for advanced breast cancer used during observation period in this study (including endocrine therapy used in combination with palbociclib) will be collected in both group.
- g. Group 1 only.
- h. “Fatigue” and “General pain” are measured as PRO-CTCAE.
- i. Baseline assessment for PRO data will be conducted after obtaining informed consent and before initiating study treatment.
- j. The observation period in this study will be 6 cycles. In Group 1 (palbociclib plus endocrine therapy), palbociclib is administered for 3 consecutive weeks followed by 1 week off treatment to comprise 1 cycle of 4 weeks. If palbociclib is temporarily interrupted (eg, due to adverse event) and the start of the next cycle is delayed, the duration of one cycle may exceed 4 weeks, then, the observation period may exceed 24 weeks. In Group 2 (endocrine monotherapy), 1 cycle is defined as 4 weeks.
- k. To be assessed at Baseline and End of study. If ECOG performance status is assessed during the observation period, the data will be entered into EDC. If patients discontinue the initiated treatment before completion of 6 cycles (eg, due to disease progression) and switch to another treatment, ECOG performance status will be assessed at end of treatment as well.

PFIZER CONFIDENTIAL

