9.1.3.1. Data sources

Data for this study will be obtained via the following sources:

- **Patient medical information:** The investigator or designated study site staff will record clinical and treatment data from patients' medical records into an eCRF promptly at baseline, during the observational period, and at the end of the observational period. Types of data to be obtained from patient medical records are described in Section 6 "Schedule of Activities".

- **Patient-Reported Outcome data:** All patients will be asked to complete a baseline questionnaire, as well as series of questions at weekly, and cycle-based intervals via a smartphone-based application downloaded onto their smartphones. PRO data entered in smartphone-based application will be transferred into the server hosted by the designated PRO vendor. Two validated PRO instruments will be administered at baseline and weekly-basis (PRO-CTCAE) or cycle-basis (EORTC-QLQ-C30). Appropriate agreements with the copyright owners will be in place for use in this study.
- **Physical Activity data:** All patients will be asked to wear a wearable device to record their physical activity. Physical activity raw data will be uploaded from the device to Actigraph CentrePoint cloud during each site visit.
- **Site characteristics information:** Basic site characteristics, including geographic location, will be collected via Pfizer's internal system, if applicable.

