The PRO-CTCAE is a PRO measurement system that includes a library of questions that measure symptomatic adverse events from the patient perspective. Seventy-eight symptom terms that are common in oncology clinical trials can be evaluable with PRO-CTCAE, and each of symptom terms is assessed relative to one or more distinct attributes, including frequency, severity, and/or interference with usual or daily activities. Responses are provided on a five-point Likert scale. The linguistic and psychometric validation of the questionnaire into Japanese was conducted and Japanese translated version is available through US-NCI webpage.

Fatigue and General pain will be evaluated in this study. Fatigue is one of common adverse event observed in PALOMA studies, and General pain is one of the major symptoms for patients with ABC. Also, it is reported that these two symptoms are frequently underestimated, then these two are selected to evaluate in this study to understand day-to-day effects of ABC treatment on patients in a real-world setting.

Treatment satisfaction

Treatment satisfaction will be evaluated with single item question (eg, “How satisfied are you with your current breast cancer treatment?”). Responses are provided on a five-point Likert scale. Single item question is selected rather than validated questionnaire (eg, Cancer Therapy Satisfaction Questionnaire) considering the burden on patient regarding a number of questions.

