16.3. Definitions

16.3.1. Adverse Events

An AE is any untoward medical occurrence in a study subject administered a product or medical device; the event need not necessarily have a causal relationship with the treatment or usage. Examples of AEs include, but are not limited to:

- Abnormal test findings;
- Clinically significant signs and symptoms;
- Changes in physical examination findings;
- Hypersensitivity;
- Drug abuse;
- Drug dependency.
- Additionally, AEs may include signs and symptoms resulting from:
- Drug overdose;
- Drug withdrawal;
- Drug misuse;
- Drug interactions;
- Extravasation;

PFIZER CONFIDENTIAL

- Exposure during pregnancy (EDP);
- Exposure via breastfeeding;
- Medication error;
- Occupational exposure.

Worsening of signs and symptoms of the malignancy under study should be recorded as AEs in the appropriate section of the CRF. Disease progression assessed by measurement of malignant lesions on radiographs or other methods should not be reported as AEs.

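### The comparison of investigator AEs with PRO-CTCAE makes no use of the baseline PRO-CTCAE, so unchanged entry symptoms that investigators leave unrecorded look like under-reporting

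*SAP*

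**What the plan says.** The secondary objective in SAP 2.1 (also protocol 8.1) is: "Evaluate concordance and discordance between investigator-assessed AE versus PRO-CTCAE". The method in SAP 6.2.5 is one sentence: "Association between investigator-reported AE and patient-reported AE will be assessed using contingency table and weighted Kappa coefficient". Protocol 12.5.2 repeats it. Neither section says when a PRO-CTCAE response becomes a patient-reported AE, or how a symptom present before treatment is counted.

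On the patient side, protocol Section 11 limits the items: "Fatigue and General pain will be evaluated in this study". It describes the attributes as frequency, severity and interference with daily life. The schedule in protocol Section 6 adds a pre-treatment assessment ("Baseline assessment for PRO data will be conducted after obtaining informed consent and before initiating study treatment") and weekly follow-up ("Weekly assessment of PRO-CTCAE will be conducted based on Cycle 1 Day 1 regardless of cycle delay").

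On the investigator side, protocol 16.1 and 16.3.1 define an AE broadly, as any unwelcome medical event, related or not, collected from consent. For symptoms of the cancer itself, protocol 16.3.1 is narrower: "Worsening of signs and symptoms of the malignancy under study should be recorded as AEs in the appropriate section of the CRF".

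**The concern.** The two sources do not measure the same thing. A weekly PRO-CTCAE answer reports the level of a symptom, and none of its attributes tells a long-standing symptom from a new one. An investigator AE is an event within a collection period. For disease symptoms, the text asks for worsening.

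A patient who enters with stable pain and keeps it can be positive on PRO-CTCAE week after week. If the investigator sees no event to record, each comparison falls in the patient-yes, investigator-no cell although neither party is wrong. Such patients are foreseeable, because protocol Section 11 says that "General pain is one of the major symptoms for patients with ABC".

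The objective is to describe concordance and discordance. Without a baseline rule, a reader of the table cannot tell missed toxicity from a difference in definition. Practice on stable symptoms may also differ between sites, since nothing fixes it.

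**Working it through.** The documents give no expected kappa, agreement rate or entry prevalence, so there is no figure to reproduce. The arithmetic below is an illustration.

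**Inputs**
- *e*, the share of patients with a new or worsened symptom: 39.6%, the fatigue AE rate with palbociclib plus letrozole in protocol Section 7. It is borrowed for scale only. Rates of 28.4% and 44.1% from the same section were also tried.
- *u*, the share with an unchanged entry symptom: assumed 10 to 40%.
- *r*, the share of those that investigators nevertheless record as AEs: assumed 0, 0.5 or 1.
- Agreement on new or worsened symptoms: assumed perfect, so that any shortfall from 1 comes from entry symptoms alone.

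**Two-by-two table**
- both positive: e + ur
- patient only: u(1 − r)
- investigator only: 0
- neither: 1 − e − u

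Observed agreement is po = 1 − u(1 − r). Chance agreement is pe = (e + u)(e + ur) + (1 − e − u)(1 − e − ur). Kappa = (po − pe)/(1 − pe).

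**Worked case, u = 0.20 and r = 0**
- po = 0.80
- pe = 0.596 × 0.396 + 0.404 × 0.604 = 0.236 + 0.244 = 0.480
- kappa = (0.800 − 0.480)/(1 − 0.480) = 0.62
- patients positive 60%, investigators positive 40%

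**Same case, r = 0.5**
- po = 0.90
- pe = 0.596 × 0.496 + 0.404 × 0.504 = 0.296 + 0.204 = 0.499 (from unrounded terms)
- kappa = (0.900 − 0.499)/(1 − 0.499) = 0.80

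| Unchanged entry symptom (u) | None recorded (r = 0) | Half recorded (r = 0.5) | All recorded (r = 1) |
|---|---|---|---|
| 10% | 0.80 | 0.90 | 1.00 |
| 20% | 0.62 | 0.80 | 1.00 |
| 30% | 0.45 | 0.69 | 1.00 |
| 40% | 0.29 | 0.55 | 1.00 |

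With e at 28.4% or 44.1%, the values for r = 0 move by no more than 0.03.

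**Weighted kappa.** The plan names a weighted kappa. With grades 0 to 3 and an assumed severity split of 60/30/10 among positives, linear weights at r = 0 give 0.83, 0.68, 0.55 and 0.43. At r = 0.5 they give 0.92, 0.84, 0.77 and 0.69. Weighting softens the effect but does not remove it.

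**Adjusting one side or both.** If only new or worsened symptoms count on both sides, kappa returns to 1.00 in every row. That follows from the assumption of perfect agreement and shows only that the artefact has gone.

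If only PRO-CTCAE is adjusted, a recorded entry symptom becomes investigator-only. At u = 0.20 and r = 0.5, that cell holds 0.20 × 0.5 = 10% of patients. The table is then the u = 10%, r = 0 table with the raters swapped, so kappa is 0.80. This equals the unadjusted value, with the apparent bias reversed. At r = 1, the one-sided version falls to 0.62, against 1.00 unadjusted.

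**The case against.** The strongest reply is that the investigator side is not as narrow as the comparison suggests. The general AE definition is broad and runs from consent, and clinically significant symptoms are among its examples. Protocol 16.2.2 tells investigators to record what they observe and what patients volunteer, with no comparison to baseline. The worsening sentence covers symptoms of the malignancy only. It says what to record and does not bar stable symptoms. Medical history is a baseline variable in SAP 3.4, but nothing there excludes its terms from AE recording.

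A reader might infer that every unchanged entry symptom is discordant by definition. The documents do not support that, and the last column of the table shows no distortion when all are recorded.

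A reader might also infer that the study expects to find investigator under-reporting. Protocol Section 11 cites earlier reports of underestimation as a reason for choosing the two symptoms, and states no expected result.

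Three further points are fair:
- SAP 6.2.5 leaves the patient-reported AE variable underived, so a baseline-adjusted version is not ruled out.
- Patients are ECOG 0 or 1 and starting first- or second-line treatment (protocol 9.1.1), so entry prevalence may be low.
- The objective is secondary and descriptive in a study that protocol Section 14 calls hypothesis-generating.

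These points limit the size and certainty of the effect. They do not supply a rule. Nothing requires stable symptoms to be recorded, and on the assumptions above half-recording still leaves kappa at 0.80 with 20% of patients affected.

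**Conclusion.** The point holds as a gap in the concordance analysis. SAP 6.2.5 and protocol 12.5.2 make no use of the baseline PRO-CTCAE, so unchanged entry symptoms that investigators do not record count as patient-only discordance. In the unadjusted comparison this source of error runs one way, toward apparent investigator under-reporting.

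Its size is unknown. The loss of kappa runs from nothing, if all such symptoms are recorded, to about 0.7 (1.00 − 0.29), if none is and 40% of patients carry one. Those figures rest on assumed entry prevalence, assumed recording practice, a borrowed event rate and perfect agreement otherwise. They are not predictions for this study.

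The primary endpoints are untouched. This is a cheap improvement to one secondary objective.

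**What to change.** In SAP 6.2.5 and protocol 12.5.2:

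- Add a cross-tabulation and weighted kappa in which a PRO-CTCAE item counts, at its score, only when it exceeds that patient's baseline score, and is 0 otherwise.
- Apply the same rule to investigators in that table: count only AEs with onset or worsening after the baseline assessment.
- Report the unadjusted table and kappa alongside, so that readers see both overall symptom agreement and agreement on change.

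The cost is a few sentences and one derived variable on each side. The investigator rule needs AE onset and worsening dates. SAP 6.6 already plans to describe AE timing, but the team should confirm that the eCRF also dates grade changes. Patients without a baseline PRO-CTCAE drop out of the adjusted table, and their number should be reported. The late-baseline allowance in SAP 6.1.1.1 is written for EORTC-QLQ-C30, so the SAP should say whether it extends to PRO-CTCAE. Under protocol 12.5, the SAP may modify planned analyses, and only major changes to primary endpoints must go into an amendment. The protocol wording can therefore be aligned at the next convenient revision.
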